#### FRACTIONAL FACTORIAL SCREENING EXPERIMENT

Participants: Clinicians and managers from provider and commissioner bodies targeted by national audit programmes. We will aim to recruit 500 participants from across the UK. We plan to work with

Project title	Document	Version	Date
Improving national clinical audits	Protocol	1	11th August 2017

the four national audit programmes which are co-applicants or collaborators on this proposal: the National Comparative Audit of Blood Transfusions; the Paediatric Intensive Care Audit Network (PICANet); the Myocardial Ischaemia National Audit Project (MINAP); and the Trauma Audit & Research Network (TARN). These four NCAs will ensure sufficient diversity in audit methods, topics and targeted audiences, thereby increasing confidence that our outputs will be relevant to the wider range of NCAs. Our assessment of 23 NCA reports in 2015 indicated significant variation amongst NCAs in the delivery of feedback (e.g. specification of target audience, linkage of findings to recommendations for action). However, we will hold further discussions with HQIP and other interested national audit programmes to identify any others which (i) wish to participate in this experiment, (ii) can construct feedback modifications based on recently collected audit data, and (iii) have identified networks of feedback recipients who could potentially take part in the experiment.

Recruitment and consent. We intend to identify and recruit participants via their respective national audits and specialist societies. Three of the audits (NCA Blood Transfusions, PICANet and TARN) already conduct surveys with participating audit sites or have specialist societies than can do so whilst MINAP possesses contact details for its sites. Audit reports are also distributed to relevant commissioning bodies, e.g. specialist commissioners in the case of PICANet.

We will send email invitations via existing national audit channels and email lists (so that that the national audits contact participants rather than ourselves). Reminder emails will be sent out one and two weeks following the first email. We will include participant information and offer online vouchers and Continuing Professional Development certification for those who participate.

The invitation email to participants will contain a link to the online survey. Once the potential participant accesses the portal the on line consent information must be checked before the participant is able to access the survey. We will explain that participants are free to withdraw without needing to provide any explanation at any time during the survey. We will explain that participants will not be able to withdraw their data once their survey responses have been submitted.

Randomisation: Individual-level, stratified block randomisation with randomly varying block sizes performed centrally by trials unit using an automated system. We will stratify by audit and recipient type (e.g. clinician, commissioning).

Intervention delivery: Participants will work through one combination of six online modifications, each a separate factor with two levels (presence/absence). We will choose a fraction of the full 26 factorial (=64 packages of modifications), ideally a quarter (=16 packages) but a half (=32 packages) if this would confound important effects when the modifications are known. The particular fraction of packages will be chosen to minimise complexity of the experiment and to avoid any packages that are felt to be infeasible or undesirable. Our design will be as close to orthogonal as possible to minimise the sample size required to detect the main effect of each modification. We will undertake feasibility testing with a sample of targeted participants and a prototype online survey to assess participant burden (perceived difficulty, time taken and completion) and reduce the number of modifications if necessary. Our experience of examining the receipt of feedback across different settings is that many recipients have or allocate only limited time to rapidly assess reports and decide whether or not to act. Similarly, for the online experiment, we anticipate that participants will aim to complete their responses within limited time (e.g. around 30 minutes); we will therefore effectively simulate the types of deeper, reflective and more superficial, reactive thinking processes that typically occur on receipt of feedback in service settings [39, 40].

Participants will be given access to a password-protected web portal. Participants will work through their assigned combination of modifications and complete an online questionnaire to assess outcomes. We will advise participants that they will be responding to hypothetical but realistic scenarios based upon recent or contemporary audit data.

As well as the above vouchers and CPD certificates incentives, participants will also be able to view some 'evidence-based tips' on how to improve their own audit and feedback practice at the end of the online survey.

Outcomes: Our primary outcome is intended enactment, i.e. plans to change behaviour. We will devise a range of graded potential responses which will range from general and non-committal (e.g. 'consider reviewing and changing our practice') through to specific commitments (e.g. 'present at next team meeting and ensure we have agreed procedures for doing X'). The primary outcome approximates to behavioural intention and, as such, we will develop and pilot the outcome first using procedures set out in our manual 'Constructing Questionnaires based on the Theory of Planned

Project title	Document	Version	Date
Improving national clinical audits	Protocol	1	11th August 2017

Behaviour' [41]. Measurement of intention involves a bespoke approach as questionnaire items have to refer to the specific behaviour under investigation.

Our systematic review of the literature on intention-behaviour relations demonstrated "a predictable relationship between the intentions of a health professional and their subsequent behaviour" [42]. We know that (i) there is almost no intention-behaviour gap when intention is low, (ii) there will be an intention-behaviour gap when perceived control over the behaviour is low, and (iii) there is an intention-behaviour gap when intention to do the 'right' thing is high (only 50% of those who intend will actually act) but we believe that our measurement strategies to reduce skewness will increase that percentage. We will consider: (i) ensuring that wording of responses to reflect high intentions (e.g. 'I will make it my top priority to do X'); reducing social desirability bias associated with low intentions (e.g. 'I will use my clinical judgment in deciding whether to do X.'); and raising the cut-off point on the response scale that identifies intenders.

Secondary outcomes include comprehension (understanding of feedback data), user experience (ease of use) and preferences. Whilst these outcomes have a limited ability to predict subsequent behaviour [43], they are critical to understand in intervention development and early evaluation [29]. We also anticipate a degree of social desirability bias in responses. The randomised design will ensure that these are balanced across intervention and control conditions. However, we will aim to minimise any unintended 'loading' of potential responses, e.g. by devising general and non-committal responses which appear as socially acceptable as the specific commitments when measuring intended enactment.

We will also collect online data analytics to assess length of time spent working through each modification and the degree to which participants engage with selected modifications (e.g. working through all levels of feedback presented for a 'graded entry' modification).

Data collection: Online questionnaire completed after exposure to feedback modifications; web analytics. We will record data on the denominators for each audit and collect data on respondent characteristics (professional roles, seniority and geographical region) to inform judgments about generalisability.

The online survey will be hosted by City, University of London. We intend to use XXX software.

Data management. We will require participants to enter their names and email addresses to ensure that CPD certificates and online vouchers can be sent following survey completion. These data will be held separately from other survey response data. We do not plan to use these data for any other purpose in the research.

All data will be stored electronically on the secure 'S' drive of the University of Leeds to comply with Data Protection legislation and University of Leeds guidelines. Participants will be able to see what information is held about them by writing to the principal investigator (RF). The data will be stored 10 years after project completion. This will potentially allow other researchers or students to use our data. However, given the evolving context of healthcare and audit and feedback methods, we expect the data to be generally redundant after 10 years.

Sample size: As such, the experiment will be powered to detect main effects of small to moderate size (i.e. 0.3 SDs) for each modification, with the intention that the optimum package would result in a moderate or large effect (i.e. 0.5 SDs plus) compared to standard practice. Assuming no interaction between the effect of each modification and the audit or trust, a total of 500 participants would give 90% power to detect each important main effect using a 2-sided 5% significance test. No allowance is needed for loss to follow-up as data is collected at one time-point. This would provide about 80% power to detect main effects of 0.25 SDs and 70% to detect main effects of 0.22 SDs.

An eventual sample size of 500 respondents is achievable if we work with four national audits. Three of the national audits (NCA Blood Transfusions, MINAP and TARN) each cover 154 acute NHS Trusts in England alone, as well as other hospital sites in the devolved nations. We will aim to recruit at least one participant per site for each audit. PICAnet presently covers 34 specialist-commissioned sites and can provide multiple respondents per site.

Analysis: A linear regression will be fitted for each continuous outcome adjusting for design factors and including main effects and two-way interaction effects for modifications. Analysis will be carried out once on an intention to treat basis and point estimates and 95% confidence intervals will be reported. Sensitivity analyses will be reported including higher order interactions and simplifying the model to include only treatment effects that are statistically significant at up to a 10% level.

Project title	Document	Version	Date
Improving national clinical audits	Protocol	1	11th August 2017

Outputs: We will have a statistical model that can be used to predict the effects of a large number of single and combined modifications. This work will allow us to make evidence informed decisions about key recommended modifications tailored to different targeted people within organisations before bringing them into the field (e.g. What comparator is most likely to encourage stated enactment? Are individual-level or unit-level data more persuasive?) By virtue of having been evaluated across up to four audit programmes, we also anticipate that these feedback modifications can be adopted or adapted by a range of national audit programmes.

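### With six modifications, the preferred 16-package quarter fraction cannot estimate the stated regression with two-way interactions, and the rule for moving to 32 packages does not settle this

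*Protocol*

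**What the plan says.** All references are to Protocol section 5.1, fractional factorial screening experiment.

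- **Factors (Intervention delivery).** "Participants will work through one combination of six online modifications, each a separate factor with two levels (presence/absence"). The full factorial has 64 packages.
- **Fraction (Intervention delivery).** The plan is "ideally a quarter (=16 packages) but a half (=32 packages) if this would confound important effects when the modifications are known". The particular fraction is to keep the experiment simple and avoid packages thought infeasible or undesirable. On efficiency: "Our design will be as close to orthogonal as possible to minimise the sample size required to detect the main effect of each modification". Resolution is not mentioned.
- **Number of factors (Intervention delivery).** After feasibility testing the team may "reduce the number of modifications if necessary".
- **Main model (Analysis).** "A linear regression will be fitted for each continuous outcome adjusting for design factors and including main effects and two-way interaction effects for modifications".
- **Sensitivity (Analysis).** "Sensitivity analyses will be reported including higher order interactions", with neither order nor number given.
- **Use of the model (Outputs).** The fitted model is meant to predict what many modifications would do, singly and in combination. Section 3 says it will guide what is evaluated next.
- **Power (Sample size).** 500 participants, two-sided 5%: 90% power for a main effect of 0.3 SD, about 80% at 0.25 SD and 70% at 0.22 SD. No power is claimed for interactions.

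**The concern.** The preferred design has fewer distinct packages than the stated model has parameters. More participants per package do not help, because they replicate the same rows of the design matrix. Adjustment for audit and recipient type does not help either, because it adds columns without separating the aliased ones.

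The clause that allows a half fraction treats confounding as something to be judged once the modifications are known. For a six-factor quarter with two-way interactions in the model, confounding is already certain. What is left open is only whether the confounded terms count as important, and the Analysis paragraph enters two-way interactions without selecting among them.

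At stake is the main product of the experiment, a model that predicts untested combinations. The fraction cannot be changed once participants have been randomised, so a later analysis plan could choose which aliased term to name but could not separate the terms.

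**Working it through.** **1. The plan's own figures.** In an orthogonal two-level design each main effect compares 250 with 250, so SE = 2/√500 = 0.089 SD, whether 16 or 32 packages are used. Power ≈ Φ(d/SE − 1.96):

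| d (SD) | Stated | Recomputed |
|---|---|---|
| 0.30 | 90% | 91.8% |
| 0.25 | about 80% | 79.8% |
| 0.22 | 70% | 69.1% |

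The stated power is reproduced. A t-based check with 22 model parameters gives 91.7% at 0.3 SD.

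**2. Parameters.** Six factors give 1 intercept + 6 main effects + 15 two-way interactions (6 × 5 / 2) = 22. Adding all 20 three-way interactions gives 42.

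**3. Rank of the design matrix.**

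| Design, six factors | Packages | Main + two-way (22) | Plus all three-way (42) |
|---|---|---|---|
| Any quarter | 16 | at most 16 | at most 16 |
| Resolution IV quarter (ABCD, CDEF) | 16 | 14 | 16 |
| Half, I = ABCDEF | 32 | 22 | 32 |
| Full | 64 | 22 | 42 |

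The ceiling of 16 follows from having 16 distinct rows. A search of the regular quarters and 5,000 random 16-package subsets found nothing above it.

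**4. Aliasing in the resolution IV quarter.** With ABCD and CDEF as defining words, the sets are AB=CD=EF, AC=BD, AD=BC, AE=BF, AF=BE, CE=DF and CF=DE: one triple and six pairs, covering all 15 interactions. The rank is 1 + 6 + 7 = 14.

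**5. What this does to a prediction.** Code each modification −1/+1 and take the AC=BD set, with estimated coefficient b. In every tested package x_A·x_C = x_B·x_D, so the fitted value is the same whichever term is credited. Suppose the fraction contains the all-absent package. Then modification A alone is not among the 16, because its ABCD product is −1. There x_A·x_C = −1 and x_B·x_D = +1. Crediting AC contributes −b; crediting BD contributes +b. The two predictions differ by 2b, and the data cannot choose between them. There are 64 − 16 = 48 untested packages.

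**6. Resolution III is not excluded.** Counted by defining relation, 175 regular quarters keep the six main effects distinct from each other. Of these, 15 are resolution IV (all rank 14) and 160 are resolution III. In a resolution III quarter the main-effect columns are still mutually orthogonal, so the near-orthogonality criterion can be met while some main effects are aliased with two-way interactions. With ABC and DEF, for example, A is aliased with BC. The 70 quarters that reach rank 16 are all resolution III, so higher rank alone is no guide.

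**7. Higher-order terms in the half fraction.** The 42-parameter model has rank 32. The 20 three-way terms form 10 pairs (ABC with DEF, and so on), which use the 32 − 22 = 10 spare dimensions. Four-way terms are aliased with two-way terms, and five-way terms with main effects.

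**The case against.** The fairest defence is that the protocol does not fix the quarter. It calls it ideal, provides for a half where confounding matters, and defers the choice because the modifications are not yet known. The Analysis sentence does not say that all two-way interactions are fitted; a selected set could be named in the analysis plan. The half fraction supports the main model in full.

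Much of this stands. The defect is a preference and a trigger that do not match the model, not a design already locked in error. But if some interactions are to be assumed negligible, the protocol should say so, because its model sentence makes no selection. If none are, the quarter is ruled out now.

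A reader might also infer more than the documents support:

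- **That the main effects or their power are wrong.** They are not. The power is reproduced, and in a resolution IV quarter main effects are clear of two-way interactions.
- **That only 8 of the 15 interactions are lost.** Eight is the rank deficit (22 − 14). All 15 are aliased and none is separately estimable.
- **That even the half fraction cannot support a higher-order sensitivity analysis.** It cannot carry all three-way terms, but the protocol does not promise all. It can carry 10 alias-pair contrasts.
- **That cutting the number of modifications makes matters worse.** The protocol does not say that a quarter of five factors would be run. Five factors in 16 packages (a half fraction, resolution V) fit 1 + 5 + 10 = 16 parameters with rank 16.
- **That 0/1 coding would erode main-effect power.** The protocol states no coding, and this belongs in the analysis plan.

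**Conclusion.** The point holds for six modifications. The preferred 16-package design cannot estimate the regression as written: 22 parameters against a rank of at most 16, and 14 in the resolution IV case. Predictions for untested combinations are then not determined by the data, whereas fitted values for the 16 tested packages are. The stated selection criteria would also admit a quarter in which some main effects are aliased with two-way interactions.

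This rests on reading the Analysis sentence as covering all two-way interactions. That is its plain sense, though the word is absent. With a selected set of interactions, at most one per alias set, a resolution IV quarter would be workable. The higher-order sensitivity analysis is under-specified rather than impossible. The matter should be settled before randomisation starts.

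**What to change.** Replace the quarter/half preference by a rule tied to the analysis:

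1. **If all two-way interactions are fitted:** require resolution V or higher. For six modifications this means a 32-package half fraction such as I = ABCDEF (rank 22 of 22). The particular fraction may still be chosen to avoid infeasible packages, provided the two-way model remains estimable.
2. **If 16 packages are kept for six modifications:** require resolution IV, prespecify at most one two-way interaction per alias set (at most seven), state which are assumed negligible, and limit the prediction claim in the Outputs paragraph accordingly.
3. **In either case:** restrict the higher-order sensitivity analysis to estimable contrasts and report their aliases. In the I = ABCDEF half these are the 10 three-way pairs.

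**Cost.** Option 1 needs 32 rather than 16 configurations in the portal. If each of the four audits needs its own content, that is 4 × 32 = 128 rather than 4 × 16 = 64. Cells shrink from about 31 participants per package (500/16) to about 16 (500/32), and further within strata of audit and recipient type, so balance by package is harder to keep. No extra participants are needed, and main-effect power is unchanged at about 92% for 0.3 SD. Option 2 costs only wording, but gives up separate estimates of the aliased interactions.

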### 5.2 OBJECTIVE 2. To evaluate how health care organisations respond to modifications of feedback from national audit programmes

*Design*: Case study of four localities, each involving a paired commissioner and provider, receiving modified national audit feedback. Given that the study involves experimentation, our approach is also informed by guidance on process evaluations of complex interventions [44].

Sampling: Sampling will be both purposive and pragmatic. We will purposively sample four localities, a paired commissioner and provider in each one. They will be sampled to maximise diversity, on the basis of previously documented high and low performance in relation to audit criteria. We selected performance as a sampling criterion because feedback may be more effective when baseline performance is low [11]. We will also aim to maximise the diversity of audit programmes.

We will work with two national audit programmes with contrasting approaches to feedback. For example, the National Comparative Audit of Blood Transfusions designs and conducts audits for different clinical topics on a cyclical basis (e.g. Patient Blood Management in major surgery in 2015 and use of blood products in patients with haematological malignancies in 2016) whereas other audits, such as PICANet or TARN employ, continuous monitoring and feedback. In this way, we will seek to maximise the diversity of sites and audit programmes studied (see Table below).

The selection of the two national audits will also be pragmatic. It will be guided by feasibility and their characteristics, e.g. alignment of timing for feedback aligning with the timescales for this Objective. On the basis of our own previous experience we expect to align timelines for two national audits.

Table. Sampling framework for Objective 2.

	Sites											
	Higher performing pair of provider and commissioner	Lower performing pair of provider and commissioner										
Audits	& feedback modifications from national audit 1	& feedback modifications from national audit 1										
	Higher performing pair of provider and commissioner	Lower performing pair of provider and commissioner										
	& feedback modifications from national audit 2	& feedback modifications from national audit 2										

Our decision to adopt a 2X2 design is based on necessary trade-offs between technical and practical considerations. Thus technical considerations suggest that there should be more rather than fewer localities, with single-locality studies to be avoided if at all possible. But, each additional locality adds to the costs of a study, incurred in negotiating access, data collection and analysis. Similarly, for a given sum of money, minimising the number of localities maximises the depth of findings. Maximising the number of localities, on the other hand, favours breadth over depth. Our choice of four localities rests in part on our 2X2 design and in part on our view that earlier studies of three localities would have benefitted from a fourth (e.g. HS&DR 09/1002/02).

Development of logic model: We will build a logic model to represent the pathways by which feedback can bring about changes in professional and organisational behaviour and which takes account of key contextual factors. We will base the model upon one currently being developed by BB and which is based upon an on-going meta-synthesis of findings from qualitative studies of audit and feedback interventions (Figure, next page) [45]. This model builds on existing theories and frameworks relevant

Project title	Document	Version	Date
Improving national clinical audits	Protocol	1	11th August 2017

[figure not shown]
to A&F related to feedback recipients (e.g. [46, 47]), intervention description (e.g. [48, 49]), and organisational implementation (e.g. [50, 51]). It posits that effective A&F is a cyclical process consisting of: goal setting and audit, feedback message production, perception and acceptance of feedback message, recipient desire and intention to respond, action (at both individual and organisational levels), and ultimately care quality improvement. It suggests the success of this process is determined by a number of moderating variables (e.g. characteristics of the feedback message or organisation), and that mediating variables explain how these moderating variables exert their effects (e.g. compatibility of the feedback topic or relative advantage of the feedback message).

We will review and revise this model drawing upon:

- The collective inter-disciplinary perspectives and experiences of our study team which include psychology, organisational change, audit design and delivery, and primary and secondary care.
- Empirical and theory-informed work designing feedback for current NIHR programme grants (RP-PG-1209-10040; RP-PG-1210-12010) [30, 46, 52]. The AFFINITIE interventions emphasize the importance of comprehensively addressing the feedback cycle whilst recognising that people have multiple, sometimes competing, goals, and that feedback can be aligned or misaligned with other resources, activities and policies across different levels in the healthcare system (i.e. individual, team, organisational, wider system) [53].
- Emerging outputs from Objective 1 predicting the effects of a range of single and combined feedback modifications.

The resulting updated model will guide data collection and analysis for this Objective (rather than make precise predictions about processes and outcomes), and will subsequently be refined following our empirical work.

Figure. Draft logic model representing pathways by which feedback can bring about changes in professional and organisational behaviour [45].

Interventions: Feedback modifications produced in Objective 1 and further organisational-level modifications less amenable to online experimentation. We will define the various components of planned feedback for each national audit, describing both general aspects of design and delivery and the specific feedback modifications being evaluated. We will draw upon our logic model to describe the wider known contextual features of each audit programme and understand where the specific feedback modifications under evaluation fit in.

Project title	Document	Version	Date
Improving national clinical audits	Protocol	1	11th August 2017

We appreciate that changes in embedded practices develop over long periods, but judge that an observational period of six months will allow us to observe changes in practices.

Institutional perspective: Sociological and institutional studies offer key insights here. Logic models, and other modelling approaches in the systems tradition, do not generally attempt to represent the ways in which local cultures (values and norms) influence causal or explanatory relationships. In this study we will address this point by studying the differences between work-as-imagined (reflected in our logic models) and work-as-done in practice in the four localities. A current HS&DR study by one of us (JK) is exploring this distinction in a related topic area, the use of (summary performance information in) dashboards [54].

Data collection: Data collection will be designed to follow the trail from the receipt of feedback data through to any actions taken to improve clinical care over a 6 month period. We will observe meetings and obtain relevant documents from the four organisations, e.g. observe clinical team meetings where audit data are discussed, obtain Trust board papers with agenda items on our national audits. In the four Trusts we will interview clinicians (training and consultant grades), directorate managers and board members (medical director and chief nursing officer), towards the end of the period (8 interviews per Trust, 32 in total). We will also interview lead commissioners towards the end of the period (1 per commissioner per audit, 4 in total).

Analysis: The analysis will exploit the diversity sampling, comparing and contrasting findings across localities and audits. We will use framework analysis for the meeting and documentary material to identify relevant themes, and then use these themes to inform a thematic analysis of the interview data. The analysis will focus on understanding how and why the intended effects are achieved, or why they are not. We will assess how feedback is aligned or misaligned with other activities and policies across different levels in each locality, for each audit [10].

Outputs: We will refine and annotate our logic model and define a set of 'best bet' modifications for national audits which can (i) be immediately adopted or adapted by national audit programmes to enhance their impacts and (ii) form the basis for more efficient, rigorous evaluations of cost-effectiveness. We will also produce a narrative account of the institutional perspective. Our Dissemination plan below further describes plans for an associated training manual and related support materials.

5.3 OBJECTIVE 3. To explore the opportunities, costs and benefits of UK national audit programme participation in a long-term international collaborative to improve audits through a programme of trials

Design: Semi-structured interview study.

Participants: We will purposively sample 30 staff: 10 from national audits, 10 healthcare professionals and 10 researchers with varying experience of participation in research evaluating A&F. Given that we wish to generate lessons relevant to an international audience, we will include interviewees from outside of the UK who have taken part in meetings to establish an international network for A&F research. The final number will be guided by evidence of data saturation [55].

Recruitment: We will approach potential interviewees via email, attaching an information sheet and consent form. We will ask those who wish to participate to sign the consent form and keep a copy for their own records before sending it back to us prior to interview. We will accept either an electronic or 'wet' signature as well as return of consent forms by email or post.

Before proceeding with any formal approaches to potential overseas interviewees, we will check with senior health services researchers in each country as to whether our procedures are likely to be relevant and acceptable. We anticipate mainly interviewing people from Canada, USA, Netherlands and Australia as the types of research and service improvement we are interested in predominantly go on in these countries (as well as the UK).

Development of interview schedule: We have provisionally identified a number of issues which influence the participation of national audit programmes in our current AFFINITIE programme. These include negotiating an understanding of equipoise in experimenting with enhanced feedback interventions, aligning timelines and human resources, working out the level and type of support needed to build sustainable enhancements into national audit programmes, and ensuring secure data sharing arrangements are in place for researchers to analyse audit data. However, there are likely to

Project title	Document	Version	Date
Improving national clinical audits	Protocol	1	11 th August 2017

be similar and further lessons generated from evaluations of major initiatives involving research-practice partnerships, such as NIHR Collaborations for Leadership in Applied Health Research and Care (CLAHRCs) and the former Veteran's Administration Quality Enhancement Research Initiative (VA-QUERI) [56-59]. We will therefore identify issues from both AFFINITIE and published related research on research-practice partnerships to generate a list of (i) likely costs and benefits of audit and feedback implementation laboratories and (ii) relevant barriers to and enablers of their establishment and maintenance. We will discuss and refine this list with our Reference Group (from Objective 1) and develop a framework setting out conditions, actions and outputs hypothesized to enable successful audit and feedback implementation laboratories.

Data collection: All interviews will be audio-recorded and transcribed. We will send participants copies of their interview transcripts for checking and corrections. They will be encouraged to change any responses either in the interests of accuracy or if they wish to provide additional information. After approving or returning their transcripts, we will allow a period of up to two weeks during which they can withdraw. We require this cut-off period because data analysis may have started and may be continuous during the course of the interviews.

Data analysis: The above framework will underpin a semi-structured interview schedule. We will conduct interviews face-to-face or by telephone as required. All interviews will be audio-recorded prior to framework analysis.

*Outputs*: We will identify optimal conditions for sustainable collaboration between national audit programmes and researchers as well as the opportunities, costs and benefits of national audit programme participation in future collaborative research to improve the effects of feedback.

Project title	Document	Version	Date
Improving national clinical audits	Protocol	1	11th August 2017

